4.4.1.2.2 Intensity

Intensity for unsolicited AEs will be derived according to the following classification: None, Grade 1, Grade 2, Grade 3, or Missing.

If the unsolicited AE is measurable and its preferred term is part of the list of solicited reactions, then the measurement is derived based upon and following the same rule of the intensity scales defined in the protocol for that measurable injection site or systemic reaction.

Note: the intensity could be considered “None” (not a reaction) in the analysis despite being considered a reaction by the Investigator (eg, swelling measurement > 0 mm but < 25 mm in adults).

Intensity for the other unsolicited AEs will correspond to the value reported in the CRF.

The maximum intensity corresponds to the highest intensity for a unique term.

For those participants receiving a non-study authorized/approved COVID-19 vaccine (eg, on Day X), the maximum intensity of unsolicited AE is analyzed as following:

- If an unsolicited AE with both time of onset and stop date before Day X, then the maximum intensity for that AE will be analyzed as collected in CRF.
- If an unsolicited AE with time of onset before Day X and the corresponding stop date is on or after Day X, then the maximum intensity for that AE will be analyzed as Missing.

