4.4.1.2.1 Presence

An observation was considered an event if it had at least a verbatim term and was not a Grade 0 intensity event.

Grade 0 events should be included in a separate listing “Unsolicited AEs not included in the safety analysis”.

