4.4.1.2.4 Time of Onset

Time of onset is derived from the start date of the unsolicited AE provided in the clinical database and the date of last vaccination as described in [Section 4.4.1.2.3](#):

Time of Onset = start date of the unsolicited AE – date of last vaccination before the unsolicited AE + 1

The time of onset should be considered as missing only if one or both of the dates are missing or partially missing.

The unsolicited AEs will be analyzed “Within 21 days”, which corresponds to AEs with a time of onset between 1 and 22 days or missing.

An AE with missing time of onset will be considered to have occurred just after the vaccination indicated by the visit number in “Appeared after visit” or similar filed, so will be included in these tables.

Time of onset will be displayed as follows:

- D01-D04
- D05-D08
- D09-D15
- D16 or later
- Missing

Note: To further clarify the analysis,

- Any unsolicited AEs collected throughout the study (SAEs, MAAEs, or AESIs) with time of onset > 22 days after each injection will not be presented in tables of unsolicited AEs within 21 days but only in tables of SAEs, MAAEs, or AESIs.
- Any unsolicited AEs (planned to report up to 21 days) with time of onset between 1 and 22 days or missing after each injection will be presented in the tables of unsolicited AEs within 21 days.
- Any unsolicited AEs (planned to report up to 21 days) with time of onset > 22 days after each injection will not be presented in any tables but listed separately.
- Any unsolicited AEs with null (0) or negative time of onset will be excluded from the above tables and listed separately.

Main safety analysis will include only those unsolicited AEs with time of onset before a participant received a non-study authorized/approved COVID-19 vaccine if applicable. Events with time of onset on or after the date of receiving a non-study authorized/approved COVID-19 vaccine will be listed separately.

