4.4.1.2.5 Duration

Duration is derived from the start and end dates of the unsolicited AE:

$$\text{Duration} = \text{stop date of unsolicited AE} - \text{start date of unsolicited AE} + 1$$

The duration should be considered as missing only if one or both of the start and end dates of the unsolicited AE is missing or partially missing.

For those participants receiving a non-study authorized/approved COVID-19 vaccine (eg, on Day X), the duration is categorized as following:

- If an unsolicited AE with both time of onset and stop date before Day X, then the duration for that AE will be derived same as above.
- If an unsolicited AE with time of onset before Day X and the corresponding stop date is on or after Day X, then the duration will be derived as Missing.

Duration will be displayed by period as following:

- 1-3 days
- 4-7 days
- 8 days or more
- Missing

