5.1.1.2 Statistical Methods for Primary Safety Objective

The following safety parameters will be used for the evaluation of safety. Additional parameters may be displayed as appropriate.

Solicited Reactions

Number and percentage of participants with:

- Presence of solicited injection site reactions and systemic reactions occurring up to 7 days after injection
- Each solicited reaction according to time of onset, maximum intensity, and number of days of occurrence over the solicited period

Unsolicited Events and Reactions

Number and percentage of participants with:

- Any unsolicited immediate systemic event in the 30 minutes after injection
- Any unsolicited event and reaction (using the current MedDRA version) 21 days after injection
- Any unsolicited event/reaction according to time of onset, maximum intensity, and duration

SAEs

Number and percentage of participants with:

- Any SAE within 21 days after injection and throughout the entire study according to SOC and PT, seriousness, and outcome

AESIs

Number and percentage of participants with:

- Any AESI within 21 days after injection and throughout the entire study according to SOC and PT, seriousness, and outcome

MAAEs

Number and percentage of participants with:

- Presence of MAAEs within 21 days after injection and throughout the entire study

Laboratory tests

- Presence of out-of-range biological test results up to 8 days post-last dose (ie, up to D09 for Cohort 1 and up to D30 for Sentinel Cohort and Cohort 2)
- Summary of toxicity grade shift from baseline

For descriptive purposes, the statistics presented in [Table 5.1](#) will be produced for the above safety parameters for each intervention group and each age group. The same dose-level group in Sentinel Cohort and Cohort 2 will also be pooled for analysis.

Harm analysis

Harm analysis assessed based on split of COVID-19 case will be assessed based on Safety Analysis Set (SafAS) at the time of the final analysis. Participants will be analyzed according to the study intervention they received. For the assessment, all dose-level arms will be pooled, and all placebo arms will be pooled as well.

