5.3.1.2 Causality

By convention, all events reported at the injection site (either solicited or unsolicited) will be considered as related to the administered product and then referred to as reactions. In a same way, all solicited systemic events pre-listed in the CRF are also considered as related to vaccination and will be considered as reactions. Missing causality for unsolicited non-serious AEs and SAEs will be considered at the time of analysis as related to vaccination.

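### Unsolicited AEs still ongoing at an outside COVID-19 vaccination lose their recorded grade and duration to Missing, so they leave the Grade 1-3 and 8-days-or-more rows while staying in the event counts

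*SAP*

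**What the plan says.** SAP 4.4.1.2.2 and 4.4.1.2.5 set rules for participants who receive a non-study authorized or approved COVID-19 vaccine on Day X.

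- AE that starts and stops before Day X: "then the maximum intensity for that AE will be analyzed as collected in CRF", and duration is stop date minus start date plus 1.
- AE that starts before Day X and stops on or after it: "then the maximum intensity for that AE will be analyzed as Missing". For duration, if "the corresponding stop date is on or after Day X, then the duration will be derived as Missing".

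Neither rule makes an exception for a grade or a duration already reached before Day X.

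Whether the event is counted at all is decided elsewhere. SAP 4.4.1.2.1 says "An observation was considered an event if it had at least a verbatim term and was not a Grade 0 intensity event". SAP 4.4.1.2.4 selects on onset alone: "Main safety analysis will include only those unsolicited AEs with time of onset before a participant received a non-study" vaccine. SAP 5.1.1.2 then lists among the outputs for the primary safety objective: "Any unsolicited event/reaction according to time of onset, maximum intensity, and duration".

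SAP 5.3.1.4 leaves missing grades of unsolicited non-serious AEs unimputed, and SAP 5.7 drops the complementary and sensitivity analyses of safety data.

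**The concern.** The rule blanks information that the investigator recorded, and how often it does so depends on how long the AE lasts. The AEs most likely to be ongoing on any given date are the long ones, so the 8-days-or-more row loses the very events it exists to show. An AE present for two weeks before Day X is known to belong there, yet is shown as Missing.

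The same holds for grade. If a Grade 3 AE reached its peak ten days before Day X and resolved after it, the grade is pre-Day X information, but the table shows Missing. The Grade 3 count can only fall or stay the same under this rule.

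SAP Section 1 reports that from 27 September 2021 all participants were to be unblinded so that they could decide about an authorized vaccine. This makes outside vaccination foreseeable, and its uptake could differ by arm once assignments were known.

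**Working it through.** **1. No figure to reproduce.** The documents state no count or percentage that depends on this rule. The check is of the rule's logic, followed by illustrations on assumed numbers.

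**2. What happens to a straddling AE.**
- Any-AE and within-21-days counts: kept (SAP 4.4.1.2.1, 4.4.1.2.4).
- SAE, AESI and MAAE counts: kept where applicable, because these are also selected on onset (SAP 4.4.1.3, 4.4.1.5.7, 4.4.1.5.8).
- Unsolicited AEs in the discontinuation summary: kept, because a missing grade is accepted there (SAP 4.4.1.5.6).
- Grade 1, 2 or 3 row: lost to Missing.
- Duration row, including 8 days or more: lost to Missing.

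**3. Consistency with the plan's own principle.** Protocol 4.1 and 7.1.2 and SAP 3.1 and 4.4.1 all bring data up to the outside vaccine into the analysis. For solicited reactions, SAP 4.4.1.1.2 derives maximum intensity from the daily records up to Day X, and SAP 4.4.1.1.5 counts the days of occurrence before it. For unsolicited AEs, the pre-Day X grade and duration are discarded.

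**4. Selectivity by duration.** With onset on day o and duration d, the stop day is o + d - 1. The AE straddles when o < X ≤ o + d - 1, which is d - 1 possible dates:
- 1-day AE: 0
- 2-day AE: 1
- 8-day AE: 7
- 30-day AE: 29

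To turn dates into shares, assume onset uniform on D1-D22 and Day X uniform over a window, given onset before Day X. The share set to Missing, among AEs in participants who take an outside vaccine after onset, is then:

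| Day X window | 3-day AE | 8-day AE | 14-day AE | 28-day AE |
|---|---|---|---|---|
| D2-D43 | 6% | 22% | 41% | 83% |
| D2-D90 | 2.5% | 9% | 17% | 34% |
| D2-D180 | 1% | 4% | 8% | 16% |

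**5. Effect on a Grade 3 percentage.** The inputs are the planned group size of 44 (Protocol Table 4.3), assumed counts, and Clopper-Pearson limits (SAP Section 5).
- 1/44 = 2.3%. Lower limit 1 - 0.975^(1/44) = 0.06%; upper limit is the 0.975 quantile of Beta(2, 43) = 12.0%.
- 0/44 = 0%. Upper limit 1 - 0.025^(1/44) = 8.0%.
- A larger assumed loss: 4/44 = 9.1% (2.5-21.7%) becomes 1/44 = 2.3% (0.06-12.0%) if three of the four AEs straddle Day X.

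**6. When the duration category is already certain.** The AE has been present on X - o days before Day X. If X - o is at least 8, the category is 8 days or more whatever happens afterwards. For smaller X - o, pre-Day X data alone may not settle it.

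**7. A gap.** An AE with no stop date fits neither intensity rule in SAP 4.4.1.2.2, so its grade handling is undefined. Its duration is Missing under the general rule.

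**The case against.** The best defence is that the grade cannot be cleanly cut at Day X. Solicited reactions have daily records; for unsolicited AEs the SAP uses the single value in the CRF, and no dated grades are described. The recorded maximum may have been reached after the outside vaccine, and using it could bring post-vaccine worsening into an analysis meant to exclude it. This stands: for an undated grade, Missing and a flagged grade are both imperfect. It does not justify blanking a grade known to precede Day X, and it does not touch duration where eight days had already passed.

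A second defence is that the SAP uses Missing elsewhere at the outside vaccine, for solicited overall days of occurrence and ongoing status (SAP 4.4.1.1.6, 4.4.1.1.7). That is fair, and it makes intensity the clearer inconsistency. The contrast with causality is also of limited force: "Missing causality for unsolicited non-serious AEs and SAEs will be considered at the time of analysis as related to vaccination" concerns information never recorded, not information set aside.

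Four stronger readings are tempting, and the documents do not support them:
- *Severe events are removed from the safety tables.* They are not. They stay counted, and Missing is a defined intensity class and a displayed duration row.
- *The primary safety endpoints are biased.* Those in Protocol Table 3.1 concern presence, which is unchanged. Grade and duration are descriptive breakdowns under the primary objective.
- *Many participants are affected.* No count of outside vaccinations, or of AEs ongoing at one, is given. Ordinary unsolicited AEs enter only with onset within 21 days of an injection, and inclusion criterion I05 required ineligibility for, or no intention of, outside vaccination until D43.
- *The most severe AEs are the ones lost.* The selection is on duration. That Grade 3 AEs last longer is an assumption.

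Development had already been discontinued, so no dose choice in this programme rests on these rows. The separate tables, listings and figures document may include a listing that shows the recorded grades; the SAP itself specifies none.

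**Conclusion.** The point holds as a reclassification problem. SAP 4.4.1.2.2 and 4.4.1.2.5 move straddling unsolicited AEs into Missing for grade and duration, and so discard values reached before Day X that the plan's own principle would keep. The selection on duration follows from the rule itself: 29 straddling dates for a 30-day AE against 1 for a 2-day AE. No imputation or sensitivity analysis recovers the loss.

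The size in this trial is unknown. The shares in the table rest on assumed uniform timing and apply only to participants vaccinated outside the study after AE onset. The change from 2.3% to 0% rests on one assumed lost participant in a planned group of 44, and early termination may have left actual groups smaller. This is a modest reporting flaw that is worth correcting because the correction is cheap.

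**What to change.** - **Duration.** Assign 8 days or more when Day X minus onset is at least 8 days. Use Missing only when the category is unknown. This has no downside, because the category is certain from data before Day X.
- **Intensity.** Show the maximum grade before Day X where it is dated; otherwise show the recorded CRF grade, flagged as straddling Day X. State how an AE with no stop date is handled.
- **Disclosure.** Footnote the number of straddling AEs per group, and list them with recorded grade, start and stop dates, and Day X.

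The cost is a few sentences in the SAP, minor programming and one listing. The downside is that some flagged grades may include worsening after the outside vaccine. The flag and the listing make that visible, so a reader can discount those grades.

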4.4.1.2.3 Last Vaccination

The last vaccination before an unsolicited AE is derived from the start date of the unsolicited AE provided in the clinical database and is calculated as follows:

- If an unsolicited AE has a complete start date and different to any of the vaccination dates, the start date is used to determine the last vaccination before the unsolicited AE.
- If the start date is missing or partially missing, or equal to any vaccination date, then the visit number in the “Appeared after Visit” or similar field, is used to determine the last vaccination before the unsolicited AE.

4.4.1.2.4 Time of Onset

Time of onset is derived from the start date of the unsolicited AE provided in the clinical database and the date of last vaccination as described in [Section 4.4.1.2.3](#):

Time of Onset = start date of the unsolicited AE – date of last vaccination before the unsolicited AE + 1

The time of onset should be considered as missing only if one or both of the dates are missing or partially missing.

The unsolicited AEs will be analyzed “Within 21 days”, which corresponds to AEs with a time of onset between 1 and 22 days or missing.

An AE with missing time of onset will be considered to have occurred just after the vaccination indicated by the visit number in “Appeared after visit” or similar filed, so will be included in these tables.

Time of onset will be displayed as follows:

- D01-D04
- D05-D08
- D09-D15
- D16 or later
- Missing

Note: To further clarify the analysis,

- Any unsolicited AEs collected throughout the study (SAEs, MAAEs, or AESIs) with time of onset > 22 days after each injection will not be presented in tables of unsolicited AEs within 21 days but only in tables of SAEs, MAAEs, or AESIs.
- Any unsolicited AEs (planned to report up to 21 days) with time of onset between 1 and 22 days or missing after each injection will be presented in the tables of unsolicited AEs within 21 days.
- Any unsolicited AEs (planned to report up to 21 days) with time of onset > 22 days after each injection will not be presented in any tables but listed separately.
- Any unsolicited AEs with null (0) or negative time of onset will be excluded from the above tables and listed separately.

Main safety analysis will include only those unsolicited AEs with time of onset before a participant received a non-study authorized/approved COVID-19 vaccine if applicable. Events with time of onset on or after the date of receiving a non-study authorized/approved COVID-19 vaccine will be listed separately.

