4.4.1.2 Unsolicited Adverse Events

Unsolicited AEs include non-serious unsolicited adverse events (AEs), immediate unsolicited AEs, serious adverse events (SAEs), adverse events of special interest (AESIs), and medically-attended adverse events (MAAEs). Analysis for unsolicited AEs only include those AEs collected within 21 days after each injection. SAEs, AESIs, and MAAEs collected out of this range will only be presented in the analysis of SAEs, AESIs, and MAAEs.

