4.4.1.5.8 MAAE

A MAAE is a new onset or a worsening of a condition that prompts the participant to seek unplanned medical advice at a physician’s office or Emergency Department. Physician contact made over the phone or by e-mail will be considered a physician office visit for the purpose of MAAE collection. This includes medical advice seeking during the study visit or routine medical care. This definition excludes pediatric check-ups, follow-up visits of chronic conditions with an onset prior to entry in the study and solicited reactions.

MAAEs will be analyzed during the following time periods:

- Within 21 days after each injection
- During the study (ie, all MAAEs occurred during entire the study or the cutoff date which corresponds to the date of any interim analysis)

Note: MAAEs with date of onset before first vaccination (negative time of onset) will not be included in analysis but will be listed separately.

Main safety analysis will include only those MAAEs with time of onset before a participant received a non-study authorized/approved COVID-19 vaccine, if applicable. MAAEs with time of onset on or after the date of receiving a non-study authorized/approved COVID-19 vaccine will be listed separately.

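### SAP 4.4.1.2.4 counts an adverse event with a partial start date as within 21 days of injection even when the recorded month and year prove a later onset

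*SAP*

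**What the plan says.** SAP 4.4.1.2.4 computes onset as "Time of Onset = start date of the unsolicited AE – date of last vaccination before the unsolicited AE + 1". It then says: "The time of onset should be considered as missing only if one or both of the dates are missing or partially missing". It fixes the 21-day set of unsolicited AEs by a rule "which corresponds to AEs with a time of onset between 1 and 22 days or missing". On the missing cases it adds: "An AE with missing time of onset will be considered to have occurred just after the vaccination indicated by the visit number", and it includes them in the 21-day tables.

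SAP 4.4.1.2 lists SAEs, AESIs and MAAEs among unsolicited AEs. It limits the unsolicited AE analysis to 21 days after each injection and adds: "SAEs, AESIs, and MAAEs collected out of this range will only be presented in the analysis of SAEs, AESIs, and MAAEs". A Note in 4.4.1.2.4 carries this out for these three event types: those "with time of onset > 22 days after each injection will not be presented in tables of unsolicited AEs within 21 days". A separate bullet of the Note repeats the missing-onset inclusion, but only for AEs whose planned reporting period is 21 days.

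Four other places matter:

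- SAP 4.4.1.2.3 uses the Appeared after Visit field to choose which injection an AE follows when its start date is incomplete.
- SAP 4.4.1.3, 4.4.1.5.7 and 4.4.1.5.8 give SAEs, AESIs and MAAEs their own period, "Within 21 days after each injection". They deal with negative onset but not with missing onset.
- SAP 5.3.1.5 leaves partial start dates unimputed, treats onset as missing if either the start or the stop date is incomplete, and includes such AEs by the visit at which they were collected.
- The onset display in 4.4.1.2.4 has a Missing category.

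**The concern.** Counting an AE as in-window when nothing is known about its date is a sensible safety default. The difficulty is that the rule treats a date lacking only the day as if nothing were known. Two records of the same late SAE then get opposite treatment: the fully dated one is left out of the 21-day table, and the less precise one is put in.

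Unsolicited AEs up to 21 days after injection are a primary safety endpoint (protocol Table 3.1), and the 21-day tables are read as the events closest in time to vaccination. SAEs, AESIs and MAAEs are collected throughout the study, so they are the events for which a late, partly dated onset can arise. With planned groups of 44, a single misplaced event is visible.

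**Working it through.** **1. Reproducing the plan's range.** With the SAP formula, onset on the injection day is 0 + 1 = 1, and onset 21 days later is 21 + 1 = 22. This agrees with the stated range of 1 to 22.

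**2. Applying the rule to partial dates.** The injection date of 1 June 2021 is assumed for illustration. The last column applies the same formula to the earliest and latest dates that the record allows.

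| Recorded start | Onset under the SAP | In 21-day table? | Possible onset days |
|---|---|---|---|
| 15 Nov 2021 | 168 | No | 168 |
| Nov 2021, day unknown | Missing | Yes | 154 to 183 |
| Jul 2021, day unknown | Missing | Yes | 31 to 61 |
| Jun 2021, day unknown | Missing | Yes | 1 to 30 |

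The November and July records cannot lie in the window, yet both are counted. The June record is ambiguous, and including it is reasonable. Checked for every injection date in 2021, an onset month two or more calendar months after the injection month always lies outside the window.

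**3. Whether anything removes the late record.**

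- The Note's exclusion of late SAEs, MAAEs and AESIs needs a computed onset above 22. A missing onset cannot meet that test.
- The Note's bullet on missing onset covers only AEs planned to be reported up to 21 days. No bullet covers an SAE, AESI or MAAE with missing onset, which leaves the general sentences above the Note. Those are unrestricted, and 4.4.1.2 puts these events within unsolicited AEs.
- The visit field selects the injection (4.4.1.2.3). It does not test the window.
- SAP 5.3.1.5 does not impute the date.

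**4. The stop date.** In 4.4.1.2.4 the two dates that determine onset are the AE start date and the injection date. SAP 5.3.1.5 instead names the start and stop dates. Read literally, a late SAE with a complete start date that is still ongoing has missing onset, and so could be counted within 21 days. The two sections conflict.

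**5. How much follow-up lies outside the windows.** Follow-up was shortened to six months (SAP section 1 and 5.7), that is, to D181 in Cohort 1 and D202 for two injections. One injection has a window of 22 days (D01 to D22). Two injections have windows D01 to D22 and D22 to D43, which is 43 days when D22 is counted once.

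- Cohort 1: (181 − 22)/181 = 159/181 = 88% outside.
- Two injections: (202 − 43)/202 = 159/202 = 79% outside.

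These are shares of follow-up days, not of events.

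**6. Effect of one event.** In a planned group of 44 (protocol Table 4.3), with Clopper-Pearson limits as in the SAP:

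- 0/44 = 0% (95% CI 0 to 8.0%)
- 1/44 = 2.3% (95% CI 0.06 to 12.0%)

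**The case against.** **The default is deliberately conservative.** It matches other SAP conventions: a missing Immediate field is taken as within 30 minutes (5.3.1.1), and missing causality as related (5.3.1.2). Any error over-reports early events. This stands as a reason to keep the default when the date is uninformative. It does not justify inclusion when the recorded month excludes the window.

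**The Note may restrict the rule.** It attaches missing onset only to AEs planned to be reported up to 21 days, and 4.4.1.2 plainly means late SAEs, AESIs and MAAEs to stay out. This shows that the intent is sound. The text still gives no rule for such an event when its onset is missing.

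**SAP 5.3.1.5 may supply a visit-based guard.** Inclusion by the visit collected could be read that way, but no late-visit exclusion is defined.

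**The events remain identifiable.** A reader might infer that they are displayed as early onsets. They are not: they fall in the Missing row of the onset display. They do count in the 21-day totals.

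**The practical consequence is limited.** The analyses are descriptive, development was discontinued, data are reviewed before lock (SAP 5.6), and the tables document is not public. SAEs must be reported to the sponsor within 24 hours, which favours complete dates. All of this stands, and it limits the weight of the point.

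**Conclusion.** The point holds on the SAP's general wording. An unsolicited AE with a partial start date is counted within 21 days even when its known month and year prove otherwise. A late SAE, AESI or MAAE lacking only the day can enter the 21-day totals, against the intent of 4.4.1.2. The conflict between 4.4.1.2.4 and 5.3.1.5 over the stop date adds a second route. The direction is over-counting of early events.

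The size is one event per affected record, or 2.3 percentage points in a planned group of 44. The number of such records cannot be derived from the documents. The 88% and 79% figures show only that most six-month follow-up days lie outside the windows.

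Three stronger readings are tempting but not supported:

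- *That the same rule governs the separate 21-day rows for SAEs, AESIs and MAAEs.* Sections 4.4.1.3, 4.4.1.5.7 and 4.4.1.5.8 give no missing-onset rule, so this is a gap rather than a stated error.
- *That undated events pass the filter requiring onset before an outside COVID-19 vaccine.* The SAP does not say how a missing onset is compared with that date.
- *That a given share of events is misplaced.* Such a figure needs a partial-date frequency, which neither document gives. The move to safety calls does not show that days of onset were often lost.

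**What to change.** Four changes to the wording:

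1. In SAP 4.4.1.2.4, count an AE with a missing or partial start date as within 21 days unless the known month and year, or the Appeared after Visit value, exclude onset 0 to 21 days after the last injection. Keep inclusion as the default whenever the available information does not exclude the window.
2. State that this rule also applies to the 21-day rows for SAEs, AESIs and MAAEs.
3. In SAP 5.3.1.5, remove the stop date from the condition that makes onset missing, so that it agrees with 4.4.1.2.4.
4. Apply the same earliest-possible-date check at the outside-vaccine cut-off, where no rule for missing onset is given.

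The cost is a few sentences and one extra programming condition on data already collected. The 21-day counts become slightly less conservative. Events excluded by the check remain in the whole-study SAE, AESI and MAAE tables, or in the listing for other unsolicited AEs.
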